12.8 List of Abbreviations

Abbreviation/Term	Definition
1L	First-line
3L/3L+	Third-line
5-FU	5-fluorouracil
AE	Adverse Event
ADA	Anti-Drug Antibodies
ALT	Alanine Aminotransferase
APaT/ASaT	All Patients/Subjects as Treated Population
AST	Aspartate Aminotransferase
β-HCG	Beta Human Chorionic Gonadotropin
CBC	Complete Blood Count
CI	Confidence Interval
CIS	Carcinoma in situ
CR	Complete Response
CrCl	Calculated Creatinine Clearance
CRF	Case Report Form
CSR	Clinical Study Report
CT	Computed Tomography
CTCAE	Common Toxicity Criteria for Adverse Events
CTLA-4	Cytotoxic T-Lymphocyte-Associated Antigen-4
CTU	Computed Tomography Urography
DL	Dose Level
DLT	Dose Limiting Toxicity
DNA	Deoxyribonucleic acid
DOCR	Duration of Complete Response
ECI	Events of Clinical Interest
ECG	Electrocardiogram
ECOG	Eastern Cooperative Oncology Group
EORTC	European Organisation for Research and Treatment of Cancer
ERC	Ethics Review Committee
FAS	Full Analyses Set
FBR	Future Biomedical Research
FDA	Food and Drug Administration
FDAAA	Food and Drug Administration Amendments Act
FDAMA	Food and Drug Administration Modernization Act
FFPE	Formalin-fixed Paraffin Embedded
GCP	Good Clinical Practice
GFR	Glomerular Filtration Rate
HCV	Hepatitis C
HIV	Human Immunodeficiency Virus

Abbreviation/Term	Definition
ICF	Informed Consent Form
ICH	International Conference on Harmonization
IHC	Immunohistochemistry
INR	International Normalized Ratio
irAEs	Immune-related Adverse Events
IRB	Institutional Review Board
ITIM	Immunoreceptor Tyrosine-based Inhibition Motif
ITSM	Immunoreceptor Tyrosine-based Switch Motif
ITT	Intent-to-Treat
IV	Intravenous
IVRS/IWRS	Interactive Voice Response System/Interactive Web Response System
KM	Kaplan-Meier
mAb	Monoclonal Antibody
mcL	Microliters
MEL	Melanoma
mg	Milligram
mg/kg	Milligram per Kilogram
mL	milliliter
MRI	Magnetic Resonance Imaging
miRNA	Micro RNA
mRNA	Messenger RNA
mTPI	Modified Toxicity Probability Interval
MSD	Merck Sharp & Dohme Corp., a subsidiary of Merck & Co., Inc.
NA or N/A	Not Applicable
NCI	National Cancer Institute
NSAID	Non-Steroidal Anti-inflammatory Drug
NSCLC	Non-small Cell Lung Cancer
ORR	Objective Response Rate
OS	Overall Survival
OTC	Over-the-counter
PBPK	Physiologically Based Pharmacokinetic
PD	Progressive Disease
PD-1	Programmed death-1
PD-L1	Programmed death-ligand 1
PFS	Progression Free Survival
PGt	Pharmacogenetic
PK	Pharmacokinetic
PK/PD	Pharmacokinetic-Pharmacodynamic
PO	Oral Administration
PR	Partial Response
RECIST	Response Evaluation Criteria in Solid Tumors

Abbreviation/Term	Definition
irRECIST	Immune-related RECIST
RNA	Ribonucleic Acid
Q2W	Every 2 Weeks
Q3W	Every 3 Weeks
SAC	Scientific Advisory Committee
SAE	Serious Adverse Events
SAP	Statistical Analysis Plan
SGOT	Serum Glutamic Oxaloacetic Transaminase
SGPT	Serum Glutamic Pyruvic Transaminase
SOC	Standard of Care
TIL	Tumor-Infiltrating Lymphocytes
TSH	Thyroid Stimulating Hormone
ULN	Upper Limit of Normal
WHO	World Health Organization

1. INTRODUCTION

This supplemental SAP (sSAP) is a companion document to the protocol. In addition to the information presented in the protocol SAP which provides the principal features of confirmatory analyses for this trial, this supplemental SAP provides additional statistical analysis details/data derivations and documents modifications or additions to the analysis plan that are not “principal” in nature and result from information that was not available at the time of protocol finalization.

2. SUMMARY OF CHANGES

This is the original sSAP and thus no changes are indicated here.

3. ANALYTICAL AND METHODOLOGICAL DETAILS

3.1 Statistical Analysis Plan Summary

Key elements of the statistical analysis plan are summarized below; the comprehensive plan is provided in [Sections 3.2](#) to [Section 3.12](#).

Study Design Overview	A Phase II Clinical Trial of Pembrolizumab as Monotherapy and in Combination with Cisplatin+5-Fluorouracil in Subjects with Recurrent or Metastatic Gastric or Gastroesophageal Junction Adenocarcinoma (KEYNOTE-059)
Treatment Assignment	Treatment assignment is open label.
Analysis Populations	Efficacy: All Subjects as Treated (ASaT) Safety: All Subjects as Treated (ASaT)
Primary Endpoint(s)	Cohort 2: Safety and tolerability (see Section 4.2.1.2) Cohort 1: objective response rate (ORR) per RECIST 1.1 assessed by central imaging vendor Cohort 3: Objective response rate (ORR) per RECIST 1.1 assessed by central imaging vendor
Statistical Methods for Key Efficacy Analyses	Cohort 1 (3L+ gastric cancer subjects/monotherapy): 95% CI for ORR will be calculated using Exact method based on binomial distribution. Cohort 2 (1L gastric cancer subjects/combination treatment): The primary objective is safety evaluation, and the secondary objective is the estimation of the ORR. 95% CI for ORR will be calculated using Exact method based on binomial distribution. Cohort 3 (1L gastric cancer subjects/monotherapy): 95% CI for ORR will be calculated using Exact method based on binomial distribution.
Statistical Methods for Key Safety Analyses	Count and percentage of AE will be provided.
Interim Analyses	For Cohort 1, an interim analysis will be performed for PD-L1 negative subjects in this study. Results will be reviewed by an external data monitoring committee. The interim analysis is summarized below. Details are provided in Section 3.7. 
 • Interim Analysis 1: 
 ○ Timing: To be performed when ~40 all-comer subjects have response assessment available ○ Testing: Futility check based on ORR assessed by central imaging vendor in PD-L1 negative subjects
Multiplicity	This is an estimation study. No multiplicity adjustment will be applied.
Sample Size and Power	Cohort 1 (3L+ gastric cancer subjects/monotherapy): Since the futility criterion was not met, the overall sample size for Cohort 1 is approximately 210. The enrollment of Cohort 1 will stop when at least 80 all-comer subjects meeting the revised eligibility criteria are enrolled. Cohort 2 (1L gastric cancer subjects/combination treatment): There will be approximately 18 subjects enrolled. Cohort 3 (1L gastric cancer subjects/monotherapy): There will be ~25 PD-L1 positive subjects enrolled in Cohort 3.

3.2 Responsibility for Analyses/In-House Blinding

The statistical analysis of the data obtained from this study will be the responsibility of the Clinical Biostatistics department of the SPONSOR.

This trial is being conducted as an open-label study. There is no randomization in the study. The Clinical Biostatistics department will generate the allocation schedule.

One planned interim analysis for Cohort 1 is described in Section 8.7. The study team will remain blinded to the PD-L1 expression level (positive or negative) for the subjects participating in the initial all-comers portion of Cohort 1 until the interim analysis of Cohort 1. Results of the interim analysis will be provided by the external unblinded statistician to the Data Monitoring Committee (DMC). The DMC will serve as the primary reviewer of the results of the interim analysis and will make recommendations in terms of whether to resume the enrollment of the PD-L1 negative subjects in Cohort 1 to the SPONSOR. Prior to study completion, the external unblinded statistician will not be involved in any discussions regarding modifications to the protocol, statistical methods, identification of protocol violators, or data validation efforts after the interim analyses. Analyses or summaries of PD-L1 biomarker status before the interim analysis will be limited and documented after the interim analysis. Following the interim analysis, the Sponsor will be unblinded to PD-L1 data.

3.3 Hypotheses/Estimation

This is an estimation study. Objectives of the study are stated in [Section 3.0](#).

3.4 Analysis Endpoints

3.4.1 Efficacy Endpoints

Objective Response Rate (ORR): proportion of subjects in the analysis population who have complete response (CR) or partial response (PR).

Duration of Response (DOR): for subjects who demonstrate CR or PR, duration of response is defined as the time from first documented evidence of CR or PR until disease progression or death due to any cause, whichever occurs first.

Disease Control Rate (DCR): for 1L subjects, DCR is defined as proportion of subjects in the analysis population who have CR or PR or stable disease (SD) for at least 6 months; for 3L+ subjects, DCR is defined as proportion of subjects in the analysis population who have CR or PR or stable disease (SD) for at least 2 months.

Progression-Free Survival (PFS): time from Day 1 Cycle 1 treatment administration to the first documented disease progression or death.

Overall Survival (OS): time from Day 1 Cycle 1 treatment administration to death due to any cause.

3.4.2 Safety Endpoints

The primary safety objective of this trial is to characterize the safety and tolerability of pembrolizumab in subjects with gastric cancer. The primary safety analysis will be based on subjects who experienced toxicities as defined by CTCAE criteria. Safety will be assessed by quantifying the toxicities and grades experienced by subjects who have

received pembrolizumab, including serious adverse events (SAEs) and events of clinical interest (ECIs).

Safety will be assessed by reported adverse experiences using CTCAE, Version 4.0. The attribution to drug, time-of-onset, duration of the event, its resolution, and any concomitant medications administered will be recorded. AEs will be analyzed including but not limited to all AEs, SAEs, fatal AEs, and laboratory changes. Furthermore, specific immune-related adverse events (irAEs) will be collected and designated as immune-related events of clinical interest (ECIs) as described in Section 7.2.3.2. Consider referring to Section 4.2.3 for the initial description of safety measures

3.5 Analysis Populations

3.5.1 Efficacy Analysis Populations

The All Subjects as Treated (ASaT) population will be used for the analysis of ORR, DCR, PFS, and OS. ASaT population consists of all subjects who received at least one dose of study treatment.

The analysis population for DOR consists of responders.

3.5.2 Safety Analysis Populations

The All Subjects as Treated (ASaT) population will be used for the analysis of safety data in this study.

At least one laboratory or vital sign measurement obtained subsequent to at least one dose of study treatment is required for inclusion in the analysis of each specific parameter. To assess change from baseline, a baseline measurement is also required.

3.6 Statistical Methods

3.6.1 Statistical Methods for Efficacy Analyses

In Cohorts 1 and 3, the primary endpoints are ORR per RECIST 1.1 assessed by central imaging vendor for all subjects and in PD-L1 positive subjects. The point estimate and 95% confidence interval will be provided using exact binomial method proposed by Clopper and Pearson (1934). Subjects in the primary analysis population (ASaT) without ORR data will be counted as non-responder.

In Cohort 1, the co-primary endpoint for PMDA submission is the 6-month overall survival rate (OS6) for all subjects and in PD-L1 positive subjects. The estimate of OS6 and 95% confidence interval will be provided using Kaplan-Meier method.

For DOR, Kaplan-Meier (KM) curves and median estimates from the KM curves will be provided as appropriate. Censoring rules for DOR are summarized in [Table 1](#).

Table 1 Censoring Rules for DOR

Situation	Date of progression or censoring	Outcome
No progression nor death, no new anti-cancer therapy initiated	Last adequate assessment	Censor (non-event)
No progression nor death, new anti-cancer therapy initiated	Last adequate assessment before new anti-cancer therapy initiated	Censor (non-event)
Death or progression after ≥ 2 consecutive missed adequate disease assessments	Last adequate assessment prior to ≥ 2 missed adequate disease assessments	Censor (non-event)
Death or progression after ≤ 1 missed adequate disease assessments	Death or progression	End of response (Event)
Patients are considered to have an ongoing response if censored, alive, have not progressed, have not started a new anti-cancer therapy and have not been determined to be lost to follow-up.		

For each cohort, the efficacy endpoints, analysis population, and statistical methods (including missing data handling) that will be employed for the efficacy analyses are presented in [Table 2](#).

Table 2 Summary of Analysis Strategy for Efficacy Endpoints

Endpoint	Statistical Method	Analysis Population	Missing data approach
ORR 
 RECIST 1.1, central imaging vendor RECIST 1.1, investigator irRECIST 1.1, central imaging vendor 	Exact method based on binomial distribution	FAS in all below populations: Cohort 1* 
 all PD-L1+ Cohort 2 
 all PD-L1+ Cohort 3 (PD-L1+ only)	Subjects with missing data are considered non-responders
OS	Summary statistics using Kaplan-Meier method	ASaT in all below populations: Cohort 1 
 all PD-L1+ Cohort 2 
 all PD-L1+ Cohort 3 (PD-L1+ only)	Censored at last assessment date
DCR 
 RECIST 1.1, central imaging vendor RECIST 1.1, investigator irRECIST 1.1, central imaging vendor 	Exact method based on binomial distribution	ASaT in all below populations: Cohort 1 
 all PD-L1+ Cohort 2 
 all PD-L1+ Cohort 3 (PD-L1+ only)	Subjects with missing data are considered as disease not under control
PFS 
 RECIST 1.1, central imaging vendor RECIST 1.1, investigator irRECIST 1.1, central imaging vendor 	Summary statistics using Kaplan-Meier method	ASaT in all below populations: Cohort 1 
 all PD-L1+ Cohort 2 
 all PD-L1+ Cohort 3 (PD-L1+ only)	Censored at last assessment date
DOR 
 RECIST 1.1, central imaging vendor RECIST 1.1, investigator irRECIST 1.1, central imaging vendor 	Summary statistics using Kaplan-Meier method	Responders in all below populations: Cohort 1 
 all PD-L1+ Cohort 2 
 all PD-L1+ Cohort 3 (PD-L1+ only)	Censored at last assessment date
HRQOL assessments	Summary statistics	ASaT in all below populations: Cohort 1 
 all PD-L1+ Cohort 2 
 all PD-L1+ Cohort 3 (PD-L1+ only)	Missing data will not be included in summary
* In Cohort 1, ORR per RECIST 1.1 assessed by central imaging vendor for all subjects and in PD-L1+ subjects is considered primary; all other efficacy analyses are considered supportive.			

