8.0 STATISTICAL ANALYSIS PLAN

This section outlines the statistical analysis strategy and procedures for the study. If, after the study has begun, but prior to any unblinding, changes made to primary and/or key secondary hypotheses, or the statistical methods related to those hypotheses, then the protocol will be amended (consistent with ICH Guideline E-9). Changes to exploratory or other non-confirmatory analyses made after the protocol has been finalized, but prior to

unblinding, will be documented in a supplemental SAP (sSAP) and referenced in the Clinical Study Report (CSR) for the study. Post hoc exploratory analyses will be clearly identified in the CSR.

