As of Oct 19, 2015, an interim analysis has been performed and the external DMC has reviewed the data. The futility criterion was not met and the DMC recommended that the enrollment of PD-L1 negative subjects could be resumed.

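### Does naming 6-month survival a Cohort 1 co-primary for the PMDA submission, when the rest of the plan makes only ORR primary, call for a change to the plan?

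*Combined protocol and SAP*

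**What the plan says.** The sSAP, section 3.6.1, opens with ORR by central RECIST 1.1 review as the primary endpoint for Cohorts 1 and 3. Its next paragraph adds: "In Cohort 1, the co-primary endpoint for PMDA submission is the 6-month overall survival rate (OS6) for all subjects and in PD-L1 positive subjects". It then commits to a Kaplan-Meier estimate of OS6 with a 95% confidence interval. The Cohort 1 footnote to Table 2, later in the same section, keeps ORR primary and states that "all other efficacy analyses are considered supportive".

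Elsewhere:

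- The sSAP summary (3.1) lists, for this cohort's primary endpoint, only "Cohort 1: objective response rate (ORR) per RECIST 1.1 assessed by central imaging vendor".
- sSAP 3.4.1 defines OS as time to death from the first administration and does not list OS6 separately.
- sSAP 1 says that the document "documents modifications or additions to the analysis plan that are not" principal in nature. sSAP 2 says: "This is the original sSAP and thus no changes are indicated here".
- Protocol 8.0 sends to a supplemental SAP "Changes to exploratory or other non-confirmatory analyses made after the protocol has been finalized", if they are made before unblinding. It requires an amendment when primary or key secondary hypotheses, or their methods, change.
- Protocol 8.1 and the Table 12 footnote name only ORR as the Cohort 1 primary efficacy endpoint. Protocol 3.2 places OS among the supportive analyses.
- Protocol 8.3 and 8.8, and sSAP 3.3 and 3.8, describe an estimation study without multiplicity adjustment.

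**The concern.** Endpoint status is normally fixed before the data are seen, and it decides what a sponsor may cite as a pre-specified primary result. Here one section supports two answers for the same quantity. The document that says co-primary also describes itself as holding no principal changes, and a co-primary endpoint for a regulatory submission is hard to call anything else. The protocol never mentions OS6.

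The timing adds to the unease. This is the first sSAP, and it reports the interim as already done: "As of Oct 19, 2015, an interim analysis has been performed and the external DMC has reviewed the data". It also says: "Following the interim analysis, the Sponsor will be unblinded to PD-L1 data". A survival endpoint that first appears after a data review in an open-label trial invites the question of whether it was chosen with results in view. If a success criterion or an error rate depended on the label, the ambiguity could decide whether Cohort 1 is read as positive.

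**Working it through.** The test is whether any number in the analysis depends on which label is right.

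**1. The plan's own Cohort 1 figure.** The only Cohort 1 planning basis is ORR precision (protocol 8.9, Table 14). Clopper-Pearson limits are the 2.5% quantile of Beta(x, n − x + 1) and the 97.5% quantile of Beta(x + 1, n − x).

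- n = 210, x = 31: 10.26% to 20.29%. The plan prints 10.3 to 20.3.
- n = 210, x = 30: lower limit 9.85%. So 31 is the smallest count with a lower limit above 10%, as stated.

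The sample size also reproduces: 42 + 33 + 135 = 210. For PD-L1 positive subjects at 50% prevalence, 21 + 33 + 67.5 = 121.5, against about 120 stated. None of this uses OS6, so its label cannot alter it.

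**2. What the label could govern.**

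- *Estimator:* Kaplan-Meier, from sSAP 3.6.1. The OS row of Table 2 uses the same method.
- *Interval:* 95%, from the same paragraph of 3.6.1. The sentence in 3.8 that promises intervals for ORR does not exclude others.
- *Populations:* all subjects and PD-L1 positive subjects, in both the OS6 sentence and the OS row.
- *Definition:* OS is defined in 3.4.1, and OS6 is that quantity read at 6 months.
- *Threshold:* none is stated for OS6.
- *Error rate:* none is allocated. Estimation only, no adjustment.
- *Data cut:* the documents tie no final cut to either endpoint.

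Every item is the same under co-primary and under supportive.

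**3. OS6 precision under either label.** The documents give no OS6 rate, so rates of 30% to 60% are assumed, with no censoring before 6 months. Then SE = √(S(1 − S)/n) and the half-width is 1.96 × SE.

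- n = 210, S = 0.5: 1.96 × √(0.25/210) = 6.8 points. Over 30% to 60% the range is 6.2 to 6.8.
- n = 120, S = 0.5: 1.96 × √(0.25/120) = 8.9 points. Over 30% to 60% the range is 8.2 to 8.9.
- Log-log limits at S = 0.5, from S^exp(±1.96·SE/(S·|ln S|)): 43.1% to 56.5% (n = 210) and 40.8% to 58.5% (n = 120).

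The label enters none of these formulas.

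**4. The amendment rule.** The trigger in protocol 8.0 is a change to a primary or key secondary hypothesis or its method. The study states no hypotheses, and ORR stays primary with its method unchanged. On its wording the rule is not triggered.

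**5. Timing.** The interim tested ORR futility in PD-L1 negative subjects (sSAP 3.7). It was not a survival analysis, and the unblinding described is to PD-L1 status. The sSAP's date is not in the text available, so when OS6 was named cannot be established from it.

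**The case for a change.** The strongest case for acting is that pre-specification is a matter of record as well as arithmetic. Someone who cites the sSAP for OS6 as co-primary can be answered from the same section, and aligning the wording would cost little. The sSAP's self-imposed limit to non-principal changes does sit badly with a new co-primary endpoint, and the amendment rule might be thought to apply by intent.

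Two parts of this stand. The Table 2 footnote has no PMDA exception, and the scope statement and the OS6 sentence fit poorly together.

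The rest does not carry. The OS6 sentence limits itself to one regulator's submission, and a specific statement can qualify a general one. Read that way, ORR is the trial's primary efficacy endpoint throughout, and OS6 has added standing in one dossier. The footnote nearly repeats the protocol's Table 12 footnote and may simply have been carried over. The scope statement names no endpoint, so it does not itself make ORR the only primary. Nothing in the documents shows that OS6 was chosen in the light of results.

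**Conclusion.** The inconsistency is real but clerical, and it does not call for a change to the plan. An analyst who follows the documents as written produces the same ORR and the same OS6, with the same intervals in the same populations, whichever label is used. The change in any estimate, interval width, threshold or error rate is zero. A report author can sensibly describe OS6 as co-primary for the PMDA submission and ORR as the primary efficacy endpoint otherwise.

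This rests on the study remaining estimation only, with no success criterion attached to OS6. The OS6 half-widths are illustrations that assume rates of 30% to 60% and complete follow-up to 6 months. The conclusion does not depend on them.

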3.6.2 Statistical Methods for Safety Analyses

Safety and tolerability will be assessed by clinical review of all relevant parameters including adverse experiences (AEs), laboratory tests, and vital signs. Counts and percentages of AEs will be provided.

3.6.3 Summaries of Baseline Characteristics, and Demographics

The number and percentage of subjects screened, enrolled, the primary reasons for screening failure, and the primary reason for discontinuation will be displayed. Demographic variables, baseline characteristics, primary and secondary diagnoses, and prior and concomitant therapies will be summarized by treatment either by descriptive statistics or categorical tables.

3.7 Interim Analyses

For Cohort 1, an interim analysis will be performed for PD-L1 negative subjects. The endpoint, timing, and purpose of the interim analyses are summarized in [Table 3](#).

The detailed process is described as below:

1. Enrollment will begin with an all-comer population. After both the PD-L1 assay is ready and ~40 all-comers enrolled, enrollment of PD-L1 positive subjects will be continued, and PD-L1 negative subject enrollment will be paused.
2. An interim analysis (reviewed by external DMC) will be performed when the initially enrolled all-comers (n~40) have response assessment available. The purpose of this interim analysis is to check treatment futility on the PD-L1 negative subjects. It is estimated that approximately 25 PD-L1 negative subjects will be included in this interim analysis.
3. If the futility criterion is not met, the PD-L1 negative subject enrollment will be resumed. The trial enrollment will end when at least 80 all-comer subjects meeting the revised eligibility criteria are enrolled. If the futility criterion is met for the PD-L1 negative subjects, the trial will continue to only enroll PD-L1 positive subjects until there are at least 90 PD-L1 positive subjects.

For the PD-L1 negative subjects, the futility criterion is met if the upper bound of the 95% confidence interval of ORR is less than 20%. If the futility criterion is met then the enrollment of PD-L1 negative subjects will not be resumed.

Among the initially enrolled ~40 all-comers, the actual number of PD-L1 negative subjects could vary depending on prevalence rate. According to the futility rule defined above, if 25 PD-L1 negative subjects are included in the interim analysis, and if no responder is observed, enrollment of PD-L1 negative subjects in Cohort 1 will not resume. Otherwise, if 1 or more responders are observed among the 25 PD-L1 negative subjects, the enrollment of the PD-L1 negative subjects will be re-opened.

Table 3: Summary of Interim Analysis Strategy

Key Endpoints for Interim Analysis	Timing of Interim Analysis	Purpose of Interim Analysis
ORR (confirmed or unconfirmed) By RECIST 1.1, central imaging vendor assessment	Initially enrolled ~40 all-comers have response assessment available (~25 PD-L1 negative subjects provided)	Check futility for PD-L1 negative subjects

As of Oct 19, 2015, an interim analysis has been performed and the external DMC has reviewed the data. The futility criterion was not met and the DMC recommended that the enrollment of PD-L1 negative subjects could be resumed.

